**Table 4 Dose-Escalation (3+3) Design**

Number of Patients with a DLT	Action
0 of 3 patients	Escalate to next dose level
1 of 3 patients	Accrue 3 additional evaluable patients at the current dose level (for a total of up to 6 evaluable patients) a
1 of 6 patients	Escalate to the next dose level
2 or more patients in a dose level group of up to 6 patients	The MTD has been exceeded

DLT = dose-limiting toxicity; MTD = maximum-tolerated dose

a For a patient to be considered “evaluable,” he must have met the minimum safety evaluation requirements of the study, and/or experienced a DLT.

#### 5.1.2 Backfill Cohorts

Pending the totality of clinical data, including but not limited, to safety and PK data, Part A cohorts which have been cleared and deemed safe may be expanded by enrolling patients into Backfill cohorts. This expanded enrollment of patients in cohorts that have cleared dose-escalation and are deemed safe is referred to as Backfilling and will further characterise the objectives for the study. The total number of patients enrolled to a Backfill cohort will not total more than 12 patients when combined with the number of patients already treated in the same cohort.

CONFIDENTIAL

Study Drug: AC176

Sponsor/Development Innovations Study Number: AC176-001/GU 207

Final Protocol: 10 July 2023 Version 4.0

Prostate cancers with AR mutations are more dependent on the AR pathway for their growth. Degradation of AR makes these cancers more susceptible to cell death. Thus, AR-mutated cancers may respond to AR degradation at lower doses than their wildtype counterparts. To enroll a patient to a Backfill cohort, there must be documentation of the AR point mutations. Patients who have not had AR mutation testing may have the testing performed after signing a pre-screening informed consent form (ICF) (see Section 7.2).

The backfill patient data will be reviewed at quarterly safety meetings. The safety data of the Backfill cohort at a specific dose level will be considered in their totality, considering the data of all patients dosed at that dose level. Toxicity for the patients enrolled into the Backfill cohort will be managed in accord with the protocol dose modification criterion described in the protocol (Section 6). Additional safety review meetings may be organized as deemed appropriate.

### 5.1.3 Dose-Limiting Toxicity

Toxicity will be assessed using NCI CTCAE Version 5.0 unless otherwise specified.

A toxicity will be considered dose-limiting if it occurs during the first cycle of treatment with AC176 during the dose-escalation phase (excluding Backfill cohort patients). Dose-limiting toxicities (DLTs) will not include any toxicity related to underlying disease (including disease progression), intercurrent illness, concomitant medications, or extraneous causes. DLTs will be defined as follows:

- Any Grade 5 toxicity
- **Hematologic:**
  - Grade 4 neutrophil count decrease for >7 days; or febrile with neutrophil count decrease (ANC <1000/mm^3 with a single temperature of >38.3°C [101°F] or a sustained temperature of ≥ 38°C [100.4°F] for more than 1 hour)
  - Grade 4 platelet count decrease; or Grade 3 platelet count decrease associated with clinically significant bleeding, including any bleeding that warrants a platelet transfusion, related to drug
  - Grade 4 anemia related to drug (life-threatening consequences requiring urgent interventions)
- **Non-Hematologic:**
  - Grade 3 or 4 non-hematologic toxicity, with the **exception of**:
    - Alopecia;
    - Grade 3 nausea, vomiting, or diarrhea if well-controlled by supportive care within 72 hours;
    - Grade 3 skin rash that improves in ≤7 days, with or without supportive care;
    - Grade 3 fatigue that improves in ≤7 days, with or without supportive care;
    - Grade 3 endocrinopathies that only require treatment with hormone replacement therapy;

*CONFIDENTIAL*

Study Drug: AC176

Sponsor/Development Innovations Study Number: AC176-001/GU 207

Final Protocol: 10 July 2023 Version 4.0

- Grade 3 non-hematologic laboratory abnormalities, other than liver function tests, will not be considered a DLT unless they are associated with clinical manifestations which lead to medical intervention and/or hospitalization.
- Potential drug-induced liver injury consistent with Hy's Law (Appendix F), defined as AST and/or ALT  $>3 \times$  ULN with concurrent total bilirubin  $>2 \times$  ULN without findings of cholestasis (alkaline phosphatase [ALP]  $>2 \times$  ULN)
- Grade 3 or higher electrolyte abnormality that lasts  $>72$  hours, unless the patient has clinical symptoms, in which case all Grade 3 or higher electrolyte abnormalities regardless of duration should count as a DLT

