- c The following parameters should be done as indicated: physical examination (including weight), Eastern Cooperative Oncology Group (ECOG) performance status, triplicate electrocardiograms (ECGs), vital signs, hematology (including absolute lymphocyte count, absolute neutrophil count, red blood cell count, reticulocytes, hemoglobin, hematocrit, platelet counts, prothrombin time/partial thromboplastin time (or aPTT [activated/PTT])/ international normalized ratio [PT/PTT/INR]), biochemistry (sodium, potassium, phosphate, chloride, creatinine, total calcium, venous bicarbonate [HCO3], albumin, total protein, aspartate aminotransferase [AST], alanine aminotransferase [ALT], alkaline phosphatase [ALP], total bilirubin, lactate dehydrogenase, glucose, creatine kinase [CK-if CK is elevated, and if it is clinically significant at the PI's discretion], then CK-MB, troponin I, and myoglobin should be reactively tested, with further follow-up as clinically warranted], urea nitrogen, and uric acid), and urinalysis. Vital signs (blood pressure, body temperature, pulse rate, and respiration rate) are checked at every visit prior to blood work and administration of treatment at the discretion of the Investigator. Safety laboratory assessments including hematology, biochemistry, coagulation and urinalysis will be performed locally. On Cycle 1 Day 8, the CBC may be performed by local laboratory as long as it can be entered into the eCRF and is approved by the Investigator. If some examinations cannot be completed at the study site, corresponding examinations should be used in replacement (e.g., CO2 vs HCO3), and this does not need to be reported as a protocol deviation.
- d Immature platelet fraction (IPF) testing will be evaluated when a patient experiences platelet count decrease, or anytime at the discretion of the physician and if the test can be run at the site. CBC counts should be collected at the same time as the IPF collection.
- e Triplicate 12-lead ECGs will be done before treatment on Cycle 1 Day 1 and Cycle 1 Day 15; before treatment on Day 1 of each subsequent cycle, at the EOT, and at any other time the Investigator deems it necessary. ECGs should be assessed before the patient takes the study drug that day, before other procedures, and after the patient has rested for at least 3 minutes. Each recording should be separated by at least 30 seconds.

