#### **5.1.4 Maximum-Tolerated Dose**

The MTD is the highest dose at which  $\leq 1$  of 6 patients experiences a DLT during Cycle 1 of therapy. If 2 or more patients in a dosing group of  $\leq 6$  patients experience a DLT, the MTD has been exceeded. If 2 or more patients in a dose level group of up to 6 patients experience a DLT and only 3 patients were evaluated at the previous (i.e., next lower) dose, then an additional 3 patients will be evaluated at this next lower dose; and, if 0 or 1 have DLTs, then this previous dose level will be declared the MTD. If 2 or more patients have DLTs, there will be further de-escalation according to the same scheme.

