**Table 6 Dose Modifications due to Grade 3 or 4 Non-Hematologic Toxicities**

Toxicity Grade	AC176 Dose a
Grade 3 (except nausea, vomiting, alopecia, diarrhea, rash, and fatigue)	Hold a until recovery to $\leq$ Grade 1 or baseline
Toxicity resolves in $\leq$ 7 days	Resume at original dose.
Toxicity resolves $>$ 7 day and $<$ 2 weeks	Reduce by 1 dose level.
Toxicity does not resolve to $\leq$ Grade 1 or baseline within 2 weeks	Discontinue treatment. If in the patient's best interest, dose may be resumed at a lower dose only after discussion and agreement with Medical Monitor.
Recurrence of the above same toxicity	Hold a until recovery to $\leq$ Grade 1 or baseline
Toxicity resolves $\leq$ 7 days	Resume at original dose or reduce by 1 dose level at the Investigator's discretion b
Toxicity resolves $>$ 7 days	Discontinue treatment. If in the patient's best interest, dose may be resumed at 1 reduced dose level only after discussion and agreement with Medical Monitor
Grade 4 (except asymptomatic electrolyte abnormalities that respond to treatment and resolve to $\leq$ Grade 2 within 72 hours, nausea, vomiting, alopecia, diarrhea, rash, and fatigue)	Discontinue treatment.
Grade 4 asymptomatic electrolyte abnormalities that respond to treatment and resolve to $\leq$ Grade 2 within 72 hours	Hold a Once resolved as mentioned, treatment may continue at 1 reduced dose level at the Investigator's discretion and upon discussion with Medical Monitor
Grade 3 or 4 nausea, vomiting diarrhea, rash, or fatigue	Hold and institute maximum supportive treatment until recovery to $\leq$ Grade 1, baseline or tolerable Grade 2
Toxicity resolves $\leq$ 7 days	Resume at original dose.
Toxicity resolves $>$ 7 day and $<$ 2 weeks	Reduce by one dose level b

Toxicity Grade	AC176 Dose a
Toxicity does not resolve to $\leq$ Grade 1 or baseline, or tolerable Grade 2 by 2 weeks	Discontinue treatment. If in the patient's best interest, dose may be resumed at a lower dose only after discussion and agreement with Medical Monitor
Recurrence of the above same toxicity	Hold and institute maximum supportive treatment until recovery to $\leq$ Grade 1, baseline or tolerable Grade 2
Toxicity resolves $\leq$ 7 days	Resume at original dose or reduce by one dose level at the Investigator's discretion b

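### Section 5.1.3 gives opposite DLT labels to an asymptomatic Grade 3 electrolyte abnormality lasting more than 72 hours, and does not say which rule governs

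*Protocol*

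**What the plan says.** Section 5.1.3 of the protocol lists what counts as a DLT in Cycle 1 of dose escalation. Three of its non-hematologic entries matter here.

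- **Umbrella criterion:** "Grade 3 or 4 non-hematologic toxicity" is a DLT, subject to listed exceptions.
- **Laboratory bullet:** "Grade 3 non-hematologic laboratory abnormalities, other than liver function tests, will not be considered a DLT", unless clinical manifestations accompany the value and lead to treatment or admission. Liver function tests are the only group taken out of this exemption.
- **Electrolyte bullet:** a DLT is a "Grade 3 or higher electrolyte abnormality that lasts" more than 72 hours. If the patient has symptoms the time limit falls away, "in which case all Grade 3 or higher electrolyte abnormalities regardless of duration should count as a DLT".

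The footnotes to the schedule of assessments (SOA 2, footnote c) place electrolytes in the safety chemistry panel: "biochemistry (sodium, potassium, phosphate, chloride, creatinine, total calcium" and so on.

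The count is used in Table 4, where DLTs in "2 or more patients in a dose level group of up to 6 patients" mean that the MTD has been exceeded, and in Section 5.1.4: "The MTD is the highest dose at which" no more than 1 of 6 patients has a DLT in Cycle 1.

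**The concern.** A persistent Grade 3 sodium, potassium, phosphate or calcium value without symptoms is a Grade 3 non-hematologic laboratory abnormality, so the laboratory bullet exempts it. It is also a Grade 3 electrolyte abnormality beyond 72 hours, so the electrolyte bullet counts it. Both statements sit in the same definition. Neither refers to the other, and neither the text on determining DLTs nor Section 5.1.4 ranks them.

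DLT is the first-listed primary endpoint and the only quantity in the escalation table. In a 3+3 design with three to six patients per dose, one reclassified patient can change the prescribed action. The label would also be argued after the event, when those deciding already know which reading permits escalation. This is not something an analysis plan could settle later, because the label drives cohort decisions while the trial is running.

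**Working it through.** The protocol gives no figure to reproduce. The check sets the two bullets side by side and then carries the label through Table 4.

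**Step 1. Does the laboratory bullet reach electrolytes?** Yes. They are measured in the biochemistry panel (SOA 2, footnote c), they are not hematologic, and they are not liver function tests, which are the only exclusion.

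**Step 2. Labels for an electrolyte abnormality**

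| Event | Laboratory bullet | Electrolyte bullet | Result |
|---|---|---|---|
| Grade 3, asymptomatic, 72 hours or less | Exempt | Criterion not met | Agree: not a DLT |
| Grade 3, asymptomatic, more than 72 hours | Exempt | DLT | **Conflict** |
| Grade 3, symptomatic, treated or admitted | Not exempt | DLT | Agree: DLT |
| Grade 4 | Silent (Grade 3 only) | Applies on its own terms | No conflict between the two bullets |

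On the bare wording there is one further mismatch: a symptomatic Grade 3 value that leads to no intervention. Section 6 calls for supportive care to relieve signs and symptoms when toxicity occurs, so a symptomatic patient would normally be treated and the laboratory exemption would lapse. That cell is close to empty and is given no weight.

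**Step 3. Is precedence stated elsewhere?** Table 6 treats electrolytes as a class of their own with a 72-hour limit: "Grade 4 asymptomatic electrolyte abnormalities that respond to treatment and resolve to" Grade 2 or lower in that time. But this row concerns Grade 4 and dose modification. It does not settle DLT status at Grade 3.

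**Step 4. Effect on the count.** Take one patient whose only event is an asymptomatic Grade 3 electrolyte abnormality lasting more than 72 hours, and apply Table 4.

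| Cohort | Laboratory bullet governs | Electrolyte bullet governs |
|---|---|---|
| 3 evaluable, no other DLT | 0/3: escalate | 0 + 1 = 1/3: add 3 patients |
| 6 evaluable, one other DLT | 1/6: escalate | 1 + 1 = 2/6: MTD exceeded |

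In the second row the reading also decides whether the dose can still be the MTD, because Section 5.1.4 allows at most one DLT in six.

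**The case against.** The best defence is that ordinary reading resolves the case. The list opens as a definition of DLTs, and the electrolyte bullet is a specific positive criterion naming grade, duration and symptoms. If the laboratory bullet governed, the duration rule would do nothing at Grade 3. The reading that gives both bullets effect is that the laboratory bullet trims the umbrella criterion and the electrolyte bullet adds a named subset back. Layout may support this. A page break falls just before the laboratory bullet and the indentation cannot be seen; nested among the umbrella's exceptions, it would qualify only that criterion.

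Most of this stands: the electrolyte bullet is the one a careful reader would apply, and it is also the cautious choice. It does not remove the contradiction. The exemption is phrased as a flat statement about DLT status, names liver function tests as its sole exclusion, and is silent on electrolytes although they too have a bullet of their own. The intended order has to be inferred.

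The safety review committee also limits the damage. It weighs the whole safety profile, may expand a cohort whatever the count, and documents its decision before new patients are dosed. That can soften an escalation decision, but it does not define the DLT count or the MTD.

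A reader might infer something stronger: that the electrolyte rules conflict broadly, including at Grade 4 or for symptomatic events, or that the chance of escalating is materially distorted. The documents do not support this. The laboratory bullet does not speak to Grade 4, symptomatic events are covered by the supportive-care instruction, and the protocol gives no rate for these events, so any change in escalation probability would rest on invented inputs.

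**Conclusion.** The contradiction is real and confined to one practical case: an asymptomatic Grade 3 electrolyte abnormality lasting more than 72 hours. Where it occurs, it can move a cohort across either decision boundary shown above; the second also requires another DLT at the same dose. The conclusion rests on electrolytes being non-hematologic laboratory values, which the schedule of assessments supports, and on the absence of any stated precedence in the DLT or MTD text. No numerical effect on escalation is claimed. Severity is minor, because the sensible reading is available and the review committee can act on the event in any case.

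**What to change.** Make two small changes to Section 5.1.3.

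1. Extend the carve-out in the laboratory bullet to read: *other than liver function tests and electrolyte abnormalities*.
2. Add: *Grade 3 electrolyte abnormalities are judged only by the electrolyte criterion: a DLT if lasting >72 hours or symptomatic; an asymptomatic Grade 3 value resolving within 72 hours is not a DLT.*

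The second change is needed because the carve-out alone could send brief asymptomatic Grade 3 values back to the umbrella criterion and make them DLTs. Grade 4 handling is unchanged.

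The cost is one phrase and one sentence, with no change to assessments, visits or sample size. The only downside is that a few events that could have been argued away will now count as DLTs.

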### **3. STUDY PATIENT POPULATION AND DISCONTINUATION**

#### **3.1 Inclusion Criteria**

Patients must meet the following criteria in order to be included in the research study:

1. Written informed consent, according to local guidelines, signed and dated by the patient or by a legal guardian prior to the performance of any study-specific procedures, sampling, or analyses.
2. Males who are at least 18 years-of-age at the time of signature of the informed consent form (ICF).
3. Patients with histological, pathological, or cytological confirmed diagnosis of advanced or metastatic castration resistant adenocarcinoma of the prostate excluding neuroendocrine differentiation or small cell features who have had disease progression per Prostate Cancer Working Group 3 (PCWG3) (Scher et al. 2016) guidance following standard treatment, including approved taxane-based chemotherapy, or who are not amenable (intolerability, patient choice) to standard therapies, or for whom no therapy of proven efficacy exists.
4. Progressive disease per PCWG3 guidance documented by either:
  - Positive bone scan (at least 2 new lesions) or metastatic lesions on computed tomography (CT)/magnetic resonance imaging (MRI) (Appendix B) that can be followed for response.

Or

- If PSA criteria is the only indication of progression, then the PSA values with a starting value of  $\geq 1.0$  ng/mL that have increased on at least 2 occasions obtained a minimum of 1 week apart.

5. Patients must have progressed on at least 2 prior approved systemic therapies (in any setting), with at least 1 being abiraterone, or enzalutamide, or apalutamide or darolutamide.
6. Patients must have had surgical or ongoing medical castration. Surgical castration is defined as bilateral orchiectomy. Medical castration is defined as ongoing ADT with a gonadotropin releasing hormone (GnRH) analog or inhibitor, plus serum testosterone level <50 ng/dL (or <1.7 nmol/L).
7. Eastern Cooperative Oncology Group (ECOG) Performance Status score of 0 to 1 (Appendix A).
8. Acceptable organ functions, as evidenced by the following laboratory data:
  - Renal function, as follows:
    - Creatinine clearance of  $\geq 50$  mL/min by the Cockcroft-Gault equation or equivalent
  - Liver function, as follows:
    - Total bilirubin  $\leq 1.5 \times$  ULN (unless the patient has Grade 1 bilirubin elevation due to Gilbert's disease or a similar syndrome involving slow conjugation of bilirubin)

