### **Determination of Dose-Limiting Toxicities**

The patient population used for determination of DLTs will consist of patients who have met the minimum safety evaluation requirements of the study, and/or who have experienced a DLT. Minimum safety requirements will be met if, during Cycle 1 of treatment, the patient receives at least 75% of planned total doses of AC176 and is observed for at least one cycle following the first dose of AC176. The minimum safety requirements must be met for a patient to be included in the MTD-determining population.

Patients who discontinue treatment early due to disease progression or withdrawal will be asked to have all end-of-treatment (EOT) safety evaluations performed as described in the protocol (see Section 7.6). If a patient withdraws from treatment during Cycle 1 due to any reason other than a DLT and does not meet the minimum requirements for inclusion in the MTD-determining population described above, that patient will be replaced.

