### 6.2.1 Specific Recommendations for Liver Function Test Abnormalities

For patients with Grade 3 liver enzyme elevations (AST/ALT), AC176 should be held until the values recover to  $\leq$  Grade 1 or baseline. Patients with an elevation of AST/ALT  $\geq 3 \times$  ULN in conjunction with a bilirubin  $\geq 2 \times$  ULN may remain in the study if a correctable, non-drug related cause of the liver test evaluations can be documented; otherwise, the patient must be discontinued from the study.

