### Definitions

#### Potential Hy's Law (PHL)

Aspartate aminotransferase (AST) or alanine aminotransferase (ALT)  $\geq 3 \times$  the upper limit of normal (ULN) together with total bilirubin (TBL)  $\geq 2 \times$  ULN at any point during the study following the start of study medication, irrespective of an increase in alkaline phosphatase (ALP).

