#### Hy's Law (HL)

Aspartate aminotransferase or ALT  $\geq 3 \times$  ULN together with TBL  $\geq 2 \times$  ULN, where no other reason other than the investigational product can be found to explain the combination of increases, e.g., elevated ALP indicating cholestasis, viral hepatitis, another drug.

For PHL and HL the elevation in transaminases must precede or be coincident with (i.e., on the same day) the elevation in TBL, but there is no specified time frame within which the elevations in transaminases and TBL must occur.

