### **Review and assessment of potential Hy's Law cases**

The instructions in this section should be followed for all cases where PHL criteria are met.

No later than 3 weeks after the biochemistry abnormality was initially detected, the Investigator will contact the Medical Monitor in order to review available data and agree on whether there is an alternative explanation for meeting PHL criteria other than DILI caused by the investigational product. The Accutar Biotechnology, Inc. Clinical Lead or equivalent and Medical Monitor will also be involved in this review, together with other subject-matter experts as appropriate.

According to the outcome of the review and assessment, the Investigator will follow the instructions below.

If there is an agreed-upon alternative explanation for the ALT or AST and TBL elevations, a determination of whether the alternative explanation is an AE will be made and subsequently whether the AE meets the criteria for a SAE:

- If the alternative explanation is not an AE, record the alternative explanation on the appropriate CRF.
- If the alternative explanation is an AE/SAE, record the AE/SAE in the CRF accordingly and follow the reporting standard practices.

If it is agreed upon that there is no explanation that would explain the ALT or AST and TBL elevations other than the investigational product:

Report an SAE (report term Hy's Law) according to the Sponsor's standard processes.

- The "Medically Important" serious criterion should be used if no other serious criteria apply.
- As there is no alternative explanation for the HL case, a causality assessment of "related" should be assigned.

If there is an unavoidable delay of over 3 weeks in obtaining the information necessary to assess whether or not the case meets the criteria for HL, then it is assumed that there is no alternative explanation until such time as an informed decision can be made:

- Report an SAE (report term Potential Hy's Law) applying serious criteria and causality assessment as per above.
- Continue follow-up and review according to the agreed-upon plan. Once the necessary supplementary information is obtained, repeat the review and assessment to determine whether HL criteria are met. Update the SAE report according to the outcome of the review, amending the reported term if an alternative explanation for the liver biochemistry elevations is determined.

*CONFIDENTIAL*

Study Drug: AC176

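### Read literally, the Hy's Law DLT bullet in 5.1.3 lets ALP above 2 × ULN from any source exclude a case; Appendix F, which it cites, excludes only when raised ALP indicates cholestasis

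*Protocol*

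**What the plan says.** Protocol 5.1.3 lists potential drug-induced liver injury consistent with Hy's Law as a DLT and refers to Appendix F. It then gives its own definition: AST and/or ALT above 3 × ULN with bilirubin above 2 × ULN, "without findings of cholestasis (alkaline phosphatase [ALP" above 2 × ULN). It does not mention where the ALP comes from or its baseline value.

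Appendix F has no ALP cut-off. Potential Hy's Law applies "irrespective of an increase in alkaline phosphatase (ALP"). Hy's Law applies "where no other reason other than the investigational product can be found to explain the combination of increases, e.g., elevated ALP indicating cholestasis".

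The other DLT route for liver tests in 5.1.3 is severity. Non-hematologic toxicity of Grade 3 or 4 is a DLT, and the laboratory exemption leaves liver tests in: "Grade 3 non-hematologic laboratory abnormalities, other than liver function tests, will not be considered a DLT" unless clinical manifestations lead to intervention or hospitalization.

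Section 6.2.1 covers AST/ALT of at least 3 × ULN with bilirubin of at least 2 × ULN and sets no ALP condition. The patient may stay only if a correctable non-drug cause is documented; "otherwise, the patient must be discontinued from the study".

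Section 3.1 accepts progression shown by "Positive bone scan (at least 2 new lesions") and limits bilirubin, AST and ALT but not ALP.

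For the MTD population, 5.1.3 requires that "the patient receives at least 75% of planned total doses of AC176" and is observed for at least one cycle. A patient who withdraws in Cycle 1 for a reason other than a DLT and misses this minimum is replaced.

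**The concern.** In metastatic prostate cancer, ALP can be raised by bone disease rather than by the liver. A patient can enter with ALP already above the level at which, read literally, the Hy's Law bullet no longer applies. If AC176 then caused liver injury below Grade 3, three parts of the protocol would treat the event differently. Section 6.2.1 would end treatment, Appendix F would report a related SAE, and 5.1.3 would record no DLT.

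Table 4 and the MTD rule in 5.1.4 run on the DLT count. A missed case could let a dose clear that the sponsor's own liver-injury standard would have counted against.

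**Working it through.** The plan gives no figure to reproduce here. The check applies the written criteria to test cases, follows the patient through the evaluability rule, and then illustrates the size.

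**1. Classification** (AST, bilirubin and ALP as multiples of ULN; AST and bilirubin taken to be below Grade 3)

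| AST | Bilirubin | ALP | 5.1.3 bullet, literal | Appendix F |
|---|---|---|---|---|
| 4 | 2.5 | 1 | DLT | Potential Hy's Law |
| 4 | 2.5 | 2.5 or 4, from bone | Not a DLT | Potential Hy's Law; Hy's Law if no other cause |
| 3 | 2 | 1 | Not a DLT (strict inequality) | Potential Hy's Law (at-least inequality) |

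The second row is the gap. The third row is a smaller mismatch: 5.1.3 uses "greater than" where Appendix F uses "at least". The CTCAE cut-offs are not in the protocol, so it is an assumption that such values can be below Grade 3. Section 6.2.1 supports it by treating Grade 3 enzyme elevations separately from this pattern.

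**2. What happens to the patient.** Full chemistry in Cycle 1 is scheduled on Day 1 and Day 15 (±2); Day 8 is a blood count only (Tables 2, 16, 17 and 18). Suppose the case is found at the Day 15 visit and dosing stops before that day's dose. Doses taken for a visit on Day 13 / 15 / 17:

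| Schedule | Taken of planned | Share | Result if not a DLT |
|---|---|---|---|
| QD | 12/14/16 of 28 | 43–57% | Replaced |
| BID | 24/28/32 of 56 | 43–57% | Replaced |
| 7 on/7 off | 7/7/9 of 14 | 50–64% | Replaced |
| 5 on/2 off | 10/10/12 of 20 | 50–60% | Replaced |
| 4 on/3 off | 8/8/10 of 16 | 50–63% | Replaced |
| 3 weeks on/1 off | 12/14/16 of 21 | 57–76% | Depends on visit day |
| 2 weeks on, 2 or 1 off | 12/14/14 of 14 | 86–100% | Evaluable, no DLT, if observed for the full cycle |

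On a replacement schedule, a case that should make a cohort 1 of 3 leaves it at 0 of 2 pending a replacement. On the 2-weeks-on schedules it reads 0 of 3.

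**3. Illustration of size.** From Table 4, with DLT probability q, a dose clears with probability (1−q)³ + 3q(1−q)⁵. Let p be the rate of other DLTs and h the rate of these cases; both are assumed.

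- Counted as DLTs: q = p + h
- Replaced: q = p/(1−h)
- Kept as non-DLT: q = p

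With p = 0.20 and h = 0.02:

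- Counted, q = 0.22: 0.4746 + 0.1906 = 0.665
- Replaced, q = 0.2041: 0.5042 + 0.1956 = 0.700
- Kept, q = 0.20: 0.5120 + 0.1966 = 0.709

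Over p = 0.10, 0.20 and 0.33, not counting the cases raises the chance of clearing a dose by:

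| Assumed h | Increase (percentage points) | Chance of at least one case in 18 to 36 patients |
|---|---|---|
| 0.5% | 0.6–1.1 | 9–17% |
| 1% | 1.3–2.2 | 17–30% |
| 2% | 2.5–4.4 | 30–52% |
| 5% | 5.9–10.9 | 60–84% |

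The last column is 1 − (1−h)ⁿ, with n from the 6 dose levels of 3 to 6 patients in 10.2. The calculation assumes that every such case is missed and that the SRC never intervenes.

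**The case against.** **The wording allows another reading.** The term that excludes is cholestasis, and the bracket may be only its usual marker. Read with Appendix F, ALP from bone is not a finding of cholestasis and the case counts. This stands as a fair reading. But the bullet offers no other criterion for cholestasis, so two investigators could classify the same case differently.

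**The gap is narrow.** This also stands. Grade 3 or 4 liver tests are DLTs whatever the ALP, and sub-Grade 3 cases above both limits with ALP up to 2 × ULN are caught. Only the subset with non-hepatic ALP above 2 × ULN is affected. The protocol does not say how often ALP reaches that level in this population, and the nonclinical summary in 1.1.1.1 names no liver toxicity, so nothing supports the upper assumed rates.

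**Safeguards remain.** A reader might infer that such a patient is left unprotected. The documents do not support that. Treatment stops under 6.2.1, the SAE is reported within 24 hours (11.2), and under 10.5.3 the SRC reviews all available safety data and may expand, de-escalate or stop. What is at risk is the formal count from which the SRC starts.

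**Open cases.** A reader might also infer that every case under review should count as a DLT from detection, because Appendix F says "it is assumed that there is no alternative explanation until such time as an informed decision can be made". That default applies only after an unavoidable delay of more than 3 weeks. Counting from detection could provisionally declare the MTD exceeded. It could also sweep in disease-related cases, since patients with liver metastases may enter with AST/ALT up to 5 × ULN.

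**Conclusion.** The point holds as a mismatch between the DLT bullet and the appendix it cites. On the literal reading, a drug-related Cycle 1 case that 6.2.1 discontinues and Appendix F calls Hy's Law can fall outside the DLT count. On QD, BID, 7/7, 5/2 and 4/3 dosing the patient is replaced and leaves the 3+3 count; on the 2-weeks-on schedules he counts as evaluable without a DLT if observed for the full cycle.

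This rests on three assumptions: the transaminase and bilirubin values can both be below Grade 3, non-hepatic ALP above 2 × ULN occurs in this population, and the case is found at the scheduled Day 15 visit. Frequency is unknown and probably low. At an assumed 0.5–1% of patients the effect on clearing a dose is 0.6–2.2 percentage points, before any SRC action. The documents do not show that the gap has occurred or that it would by itself put the MTD in error. It is worth fixing because the change is cheap and the rule governs a first-in-human escalation.

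**What to change.** Reword the bullet in 5.1.3 to AST and/or ALT at least 3 × ULN with total bilirubin at least 2 × ULN, meeting Hy's Law per Appendix F. Raised ALP should exclude a case only if it indicates cholestasis (hepatic origin, judged against baseline ALP and known bone disease) that explains the rise. State that a Cycle 1 case judged to be Hy's Law under Appendix F is a DLT, so the patient is evaluable and not replaced.

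Appendix F allows up to 3 weeks from detection before the review contact, so a case found on Day 13–17 may still be open on Day 34–38 (13 + 21 to 17 + 21), after the cycle ends. For such a case the SRC should defer the escalation decision rather than count it automatically. Section 10.5.3 already allows deferral, but words it for patients still ongoing, so one sentence should say that it covers an open liver review.

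Cost: a wording amendment with the IRB and/or FDA steps in 14.1, and an SRC recheck of earlier Cycle 1 liver cases so that all cohorts follow one rule. No scheduled visit or test is added. The price is some case-by-case judgement: the scheduled chemistry measures total ALP only, so its source must be inferred from baseline, bone disease and any further work-up.
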